### **Definition of Progressive Disease**

A composite definition of PD will be defined by first occurrence of any one of the following:

- Appearance of new metastatic lesions outside the bone
- New metastatic lesions on bone scan confirmed as described above
- Development of an indication for radiotherapy while on treatment
- Unequivocal progression of non-target lesions
- Global deterioration of health status requiring discontinuation of treatment without objective evidence of PD
- Development of an indication for non-protocol systemic therapy

Patients experiencing radiographic progression in the absence of clinical progression are allowed to remain on treatment until follow up scan confirms progression.

Note that PSA progression (as defined above) alone does not meet the criteria for progressive disease.

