### **6.5 Use of Concurrent/Concomitant Medications**

#### **6.5.1 Prohibited Concomitant Medications**

Participants are prohibited from receiving the following therapies during the Screening and Treatment Phase (including retreatment for post-complete response relapse) of this trial (see Appendix 4):

- Antineoplastic systemic chemotherapy or biological therapy other than LHRH analogue
- Immunotherapy not specified in this protocol
- Chemotherapy not specified in this protocol
- Investigational agents not specified in this protocol
- Radiation therapy
  - Note: Radiation therapy to a symptomatic solitary metastatic lesion or to the brain may be allowed at the investigator's discretion.

Live vaccines within 30 days prior to the first dose of study treatment and while participating in the study. Examples of live vaccines include, but are not limited to, the following: measles, mumps, rubella, varicella/zoster, yellow fever, rabies, BCG, and typhoid vaccine. Seasonal influenza vaccines for injection are generally killed virus vaccines and are allowed; however, intranasal influenza vaccines (e.g., FluMist®) are live attenuated vaccines and are not allowed.

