###### Progressive Disease (PD)

At least a 20% increase in the sum of the diameters of target lesions, taking as reference the smallest sum on study (this includes the baseline sum if that is the smallest on study). In addition to the relative increase of 20%, the sum must also demonstrate an absolute increase of at least 5 mm (0.5 cm). (Note: the appearance of one or more new lesions is also considered progressions).

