### 8.3.3 Secondary Analysis (or Analysis of Secondary Endpoints)

Secondary Objective 1 Analysis: AEs will be recorded and severity-graded using CTCAE version 5.0. Clinically significant laboratory, physical exam, scan, and ECG abnormalities will be captured as AEs. The frequency and severity of AEs will be descriptively reported on a per-patient analysis.

Secondary Objective 2 Analysis: The median radiographic progression-free survival determined by PCWG3 criteria

Secondary Objective 3 Analysis: PSA50 and PSA90 response are defined as above, a  $\geq 50\%$  and  $> 90\%$  decline from baseline in serum PSA, respectively, confirmed by repeat measurement  $\geq 4$  weeks later. The PSA50 and PSA 90 response proportions will be reported along with 95% confidence interval for each study cohort, for the subset of PSA-evaluable patients (serum PSA  $\geq 2$  ng/mL at baseline).

Secondary Objective 4 Analysis: Median progression-free survival will be determined for each cohort as from the date of first dose of protocol-defined therapy, using Kaplan-Meier product limit method. Progression is defined as per Section 7.1.4. The first scan time point demonstrating radiographic progression requires confirmatory scans performed  $\geq 4$  weeks after first scan time point to confirm progression. Patients who discontinue treatment for reasons other than those listed above (e.g. AE, patient withdrawal) will be censored by the date of last treatment.

Secondary Objective 5 Analysis: The median overall survival along with 95% confidence interval will be determined from the date of first dose of protocol-defined therapy until death from any cause, using the Kaplan-Meier product limit method. Patients will be followed for long-term survival as outlined in the Study Procedures. Patients who withdraw from study will be censored for analysis of overall survival using the date of study withdrawal.

Secondary Objective 6 Analysis: The objective response rate and median duration of response will be reported along with 95% confidence interval, for the subset of patients with measurable soft tissue disease by RECIST 1.1 criteria.

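### Section 8.3.3 sends PFS to Section 7.1.4, which holds two conflicting definitions of progression, and one of them does not match the rPFS endpoint

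*Combined protocol and SAP*

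**What the plan says.** **Endpoint.** Section 2.3 defines Secondary Objective 2 as time from start of treatment to PCWG3 radiographic progression or death. Secondary Objective 4 is PSA-PFS.

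**Analysis.** In Section 8.3.3 the entry for Objective 2 only repeats that median rPFS is determined by PCWG3. It gives no event list, estimator or censoring rule. The entry for Objective 4 contains the Kaplan-Meier text, the requirement for confirmatory scans, a censoring rule, and the sentence "Progression is defined as per Section 7.1.4".

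**First definition in 7.1.4.** Under the evaluation of target lesions, progression is "At least a 20% increase in the sum of the diameters of target lesions", measured from the smallest sum on study, with an absolute increase of at least 5 mm. Table 7.1 makes target-lesion progression an overall response of PD, with or without new lesions. A further subsection gives the PCWG3 bone-scan rules.

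**Second definition in 7.1.4.** Under Definition of Progressive Disease: "A composite definition of PD will be defined by first occurrence of any one of the following". Six items follow. Three are radiographic: new lesions outside bone, confirmed new bone lesions, and "Unequivocal progression of non-target lesions". Three are not: "Development of an indication for radiotherapy while on treatment", "Global deterioration of health status requiring discontinuation of treatment without objective evidence of PD" and "Development of an indication for non-protocol systemic therapy".

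**Radiotherapy.** Section 6.5.1 and Appendix 4 list radiotherapy as prohibited, with a discretionary exception: "Radiation therapy to a symptomatic solitary metastatic lesion or to the brain may be allowed".

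**The concern.** The PFS analysis points to a whole section rather than to one event definition, and that section gives two that disagree. If the closing list governs, target-lesion growth, a core RECIST criterion, is not a listed event, while three kinds of clinical event count in an endpoint named radiographic. If the RECIST and PCWG3 rules govern, the reverse holds. With the choice unstated, it could be made after the data are seen. In a trial of 24 patients each reclassified patient is 1/24, about 4% of the sample. The same PFS variable is used in the exploratory biomarker and irAE associations.

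**Working it through.** The plan gives no PFS figure to reproduce: no assumed median, event count or power. The check is a comparison of the texts, followed by one illustration of direction.

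**1. How the same patient is classified**

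| Only event observed | Target rule, Table 7.1, PCWG3 bone rules (7.1.4) | Closing list (7.1.4) | rPFS endpoint (2.3) |
|---|---|---|---|
| Target growth of at least 20% and 5 mm | PD | not listed | consistent with an event, since 7.1 uses RECIST 1.1 for progression and PCWG3 for bone |
| Non-target progression or new lesions, bone or other | PD | PD | event |
| Indication for radiotherapy | not PD | PD | not radiographic |
| Global deterioration without objective PD | reported as *symptomatic deterioration* (note to Table 7.1) | PD | not radiographic |
| Indication for non-protocol systemic therapy | not PD | PD | not radiographic |

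The two definitions agree on one row and differ on four. On global deterioration the conflict is explicit, because the note to Table 7.1 and the list name the same event and label it differently. Section 3.5 also keeps radiographic progression, clinical progression and receipt of non-protocol therapy apart as separate reasons for stopping treatment; the list merges such events into PD.

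**2. Where the governing sentence sits.** It is under Objective 4, which Section 2.3 defines as PSA-PFS. Yet it is about confirmatory scans, and 7.1.4 says that PSA progression alone is not PD. By content it reads as the missing rPFS text. As filed, rPFS has no analysis text beyond a mention of PCWG3, and PSA-PFS has a rule that does not describe it.

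**3. Censoring.** The same entry censors at last treatment those who stop for reasons other than those listed. A patient stopped under Section 3.5 for RECIST progression through target growth alone has no event on the closing list. Read that way, the patient is censored at about the time of progression, which is informative censoring.

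**4. Direction of the effect (assumed inputs).** Let the rPFS hazard be constant at λ. Let g be the share of rPFS events that are target growth only and go uncounted, and f the hazard of added clinical-only events relative to λ. The documents give neither.

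- Hazard under the list: λ(1 − g + f).
- Median = ln 2 / hazard, so list median / rPFS median = 1/(1 − g + f).
- g = 0.2, f = 0: 1/0.8 = 1.25.
- g = 0, f = 0.2: 1/1.2 = 0.83.
- g = f = 0.2: 1/1.0 = 1.00.
- Over g and f from 0 to 0.4: from 1/1.4 = 0.71 to 1/0.6 = 1.67.

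The two departures work against each other, so the net direction is not determined. The upper end is closer to a ceiling if uncounted patients stay in follow-up rather than being censored: many would soon have an indication for other systemic therapy, which is itself on the list.

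**The case against.** A reader might infer that PFS in this trial would not measure radiographic progression, or that a patient whose target lesions grow by 20% can never be a PFS event. The documents do not support either reading. The 20% and 5 mm rule is in the same Section 7.1.4 that the analysis cites, so it is missing from one list and not from the protocol. Section 7.1 sets RECIST 1.1 with PCWG3 for bone as the framework for progression. Objective 2 cites PCWG3 and does not cite the list. The sentence pointing to 7.1.4 is filed under PSA-PFS. Even if the list governed, three of its six items are radiographic, so the result would be a mixture of event types.

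A reader might also see a flat contradiction on radiotherapy. The permission is a narrow exception to a prohibition, and allowing a treatment while counting the need for it as an analysis event is not illogical. What is missing is a statement of how an on-study course within the exception is classified.

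Finally, PFS here is descriptive, with no hypothesis or decision rule, and the documents state no benchmark rPFS median against which it would be compared.

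These points limit the finding but do not remove it. None of them tells the analyst which definition applies, and the closing list still contradicts the target-lesion rule, Table 7.1 and the Section 2.3 endpoint.

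**Conclusion.** The concern holds as an unresolved conflict of definitions. The composite list in Section 7.1.4 omits an event that the same section counts as PD, adds three non-radiographic events, and does not match the rPFS endpoint. If it governs, patients with target growth only may be missed or censored at last treatment, and clinical-only events would count. This rests on the text alone. The size is not known: the ratio of 0.71 to 1.67 depends on assumed constant hazards and on shares the documents do not give, and it includes no change. The effect is confined to secondary and exploratory PFS. The composite response endpoint, the sample size and the two-stage rule do not depend on it. It should be corrected before PFS is analysed.

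**What to change.** 1. Under Secondary Objective 2 in Section 8.3.3, state one rPFS event list consistent with Sections 2.3 and 7.1 and with the target-lesion, Table 7.1 and bone-scan rules of 7.1.4: RECIST 1.1 soft-tissue progression (target growth, unequivocal non-target progression or new lesions), PCWG3 bone progression, or death. Put the Kaplan-Meier and censoring text there, and name the censoring reasons rather than referring to those listed above.
2. Report clinical-only events separately as clinical progression, outside the rPFS event list.
3. Move or correct the Objective 4 text so that it addresses PSA-PFS.
4. Reconcile Section 6.5.1 and Appendix 4, the note to Table 7.1, and the closing list of 7.1.4 on how on-study radiotherapy and symptomatic deterioration are classified in the analysis. This concerns endpoint classification; which clinical rule is right is for the investigators.

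The cost is wording in 7.1.4 and 8.3.3, with matching clarification in 6.5.1 and Appendix 4 if needed. The scheduled CT and bone scans already collect the imaging data.

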## **7.2 Evaluation of Safety**

The safety parameters for this study include all clinically significant laboratory abnormalities, clinically significant physical findings, clinically significant findings on scans and/or ECG, and spontaneous reports of AEs reported to the investigator by participants.

Toxicity will be assessed according to the NCI CTCAE version 5.0. Safety analyses will be performed for all participants from the time of first study drug administration on C1D1.

## **7.3 Definitions of Adverse Events**

### **7.3.1 Adverse Event**

An AE (also known as an adverse experience) is defined as any untoward medical occurrence associated with the use of a drug in humans, whether or not considered drug related. More specifically, an AE (can be any unfavorable and unintended sign (e.g., an abnormal laboratory finding), symptom, or disease temporally associated with the use of a drug, without any judgment about causality. An AE can arise from any use of the drug (e.g., off-label use, use in combination with another drug) and from any route of administration, formulation, or dose, including an overdose.

### **7.3.2 Adverse Reaction**

An adverse reaction is defined as any AE caused by the use of a drug. Adverse reactions are a subset of all suspected adverse reactions for which there is reason to conclude that the drug caused the event.

### **7.3.3 Suspected Adverse Reaction**

A suspected adverse reaction is defined as any AE for which there is a reasonable possibility that the drug caused the AE. For the purposes of IND safety reporting, “reasonable possibility” indicates that there is evidence to suggest a causal relationship between the drug and the AE.

A suspected adverse reaction implies a lesser degree of certainty about causality than an adverse reaction.

#### **7.3.3.1 Unexpected**

An AE or suspected adverse reaction is considered unexpected if it is not listed in the investigator brochure or package insert(s), or is not listed at the specificity or severity that has been observed, or, if an investigator brochure is not required or available, is not consistent with the risk information described in the general investigational plan or elsewhere in the current application.

“Unexpected,” as used in this definition, also refers to AEs or suspected adverse reactions that are mentioned in the investigator brochure as occurring with a class of drugs or as anticipated from the pharmacological properties of the drug, but are not specifically mentioned as occurring with the particular drug under investigation.

AEs that would be anticipated to occur as part of the disease process are considered unexpected for the purposes of reporting because they would not be listed in the investigator brochure. For example, a certain number of non-acute deaths in a cancer trial would be anticipated as an outcome of the underlying disease, but such deaths would generally not be listed as a suspected adverse reaction in the investigator brochure.

Some AEs are listed in the Investigator Brochure as occurring with the same class of drugs, or as anticipated from the pharmacological properties of the drug, even though they have not been observed with the drug under investigation. Such events would be considered unexpected until they have been observed with the drug under investigation. For example, although angioedema is anticipated to occur in some participants exposed to drugs in the angiotensin-converting enzyme inhibitor class and angioedema would be described in the investigator brochure as a class effect, the first case of angioedema observed with the drug under investigation should be considered unexpected for reporting purposes.

For apalutamide, the link to the package insert is:

<http://www.janssenlabels.com/package-insert/product-monograph/prescribing-information/ERLEADA-pi.pdf>

For cetrelimab, the expectedness of an AE will be determined by whether or not it is listed in the Investigator's Brochure.

#### **7.3.3.2 Serious**

An AE or suspected adverse reaction is considered serious if, in the view of either the investigator or sponsor, it results in any of the following outcomes:

- Death
- Life-threatening AE
- Inpatient hospitalization or prolongation of existing hospitalization
- A persistent or significant incapacity or substantial disruption of the ability to conduct normal life function
- Congenital anomaly/birth defect

Important medical events that may not result in death, are life-threatening, or require hospitalization may be considered serious when, based upon appropriate medical judgment, they may jeopardize the participant and may require medical or surgical intervention to prevent

one of the outcomes listed in this definition. Examples of such medical events include allergic bronchospasm requiring intensive treatment in an emergency room or at home, blood dyscrasias or convulsions that do not result in inpatient hospitalization, or the development of drug dependency or drug abuse.

### **7.3.3.3 Life-threatening**

An AE or suspected adverse reaction is considered life-threatening if, in the view of either the investigator or sponsor, its occurrence places the participant at immediate risk of death. It does not include an AE or suspected adverse reaction that, had it occurred in a more severe form, might have caused death.

### **7.3.3.4 Adverse Events of Special Interest**

AEs of special interest are events that the drug manufacturer is actively monitoring as a result of a previously identified signal (even if non-serious).

For cetrelimab, the AEs of special interest are:

- Immune-related reactions

There are no non-serious AEs of special interest for apalutamide.

Any AE of special interest that is to be reported to the drug manufacturer should be recorded on a Serious Adverse Event Report Form and be reported to the drug manufacturer within 24 hours of becoming aware of the event.

### **7.3.3.5 Product Quality Complaint (PQC)**

A product quality compliant is defined as any suspicion of a product defect related to a potential quality issue during manufacturing, packaging, release testing, stability monitoring, dose preparation, storage or distribution of the product, or delivery system. Not all PQCs involve a subject. Lot and batch numbers are of high significance and need to be collected whenever available.

Examples of PQC include but not limited to:

- Functional Problem: e.g., altered delivery rate in a controlled release product
- Physical Defect: e.g. abnormal odor, broken or crushed tablets/capsules
- Potential Dosing Device Malfunction: e.g., autoinjector button not working, needle detaching from syringe
- Suspected Contamination
- Suspected Counterfeit

### **7.3.3.6 Special Reporting Situations**

Safety events of interest for a J&J medicinal product that require expediting reporting and/or safety evaluation include, but are not limited to:

- Drug exposure during pregnancy (maternal and paternal)
- Overdose of a J&J medicinal product
- Exposure to a J&J medicinal product from breastfeeding
- Suspected abuse/misuse of a J&J medicinal product

- Inadvertent or accidental exposure to a J&J medicinal product
- Medication error involving a J&J medicinal product (with or without patient exposure to the J&J medicinal product, e.g., name confusion)
- Suspected transmission of any infectious agent via administration of a medicinal product

Special situations should be recorded on the Adverse Event page of the CRF.

Any special situation that meets the criteria of a serious adverse event should be recorded on a MedWatch form and be reported to the J&J within 24 hours of becoming aware of the event.

### **7.3.3.7 Pregnancy**

Because the J&J medicinal product may have an effect on sperm, pregnancies in partners of male subjects exposed to a J&J medicinal product will be reported by the PRINCIPAL INVESTIGATOR within 24 hours of their knowledge of the event using the Serious Adverse Event Form. Depending on local legislation this may require prior consent of the partner.

Follow-up information regarding the outcome of the pregnancy and any postnatal sequelae in the infant will be required.

### **7.3.4 Recording of Adverse Events**

Refer to the Data Safety Monitoring Plan, located in Appendix 2.

### **7.3.5 Follow-up of Adverse Events**

All participants who experience AEs will be followed with appropriate medical management until resolved or stabilized, as determined by the investigator, or until the initiation of new anti-cancer therapy, whichever occurs first. For selected AEs for which administration of the investigational product was stopped, a re-challenge of the subject with the investigational drug may be conducted if considered both safe and ethical by the investigator.

### **7.3.6 Adverse Events Monitoring**

Refer to the Data Safety Monitoring Plan, located in Appendix 2.

### **7.3.7 Expedited Reporting**

#### **Reporting to the Data and Safety Monitoring Committee**

If a death occurs during the treatment phase of the study or within 100 days after the last administration of the study drug(s) and it is determined to be related either to the study drug(s) or to a study procedure, the Investigator or his/her designee must notify the DSMC Chair (or qualified alternate) within 1 business day of knowledge of the event. The contact may be by phone or e-mail.

#### **Reporting to Institutional Review Board**

The UCSF PI must report events to the UCSF IRB according to institutional guidelines.

UCSF IRB website for guidance in reporting AEs: <https://irb.ucsf.edu/adverse-event>

The PI at each participating site is responsible for reporting events to the IRB of record according to IRB guidelines.

#### **Expedited Reporting to the FDA**

If the study is being conducted under an IND, the Sponsor (or the Sponsor-Investigator) is responsible for determining whether or not the suspected adverse reaction meets the criteria for expedited reporting in accordance with federal regulations (21 CFR §312.32).

The Sponsor (or Sponsor-Investigator) must report in an IND safety report any suspected adverse reaction that is both serious and unexpected. The Sponsor needs to ensure that the event meets all three definitions:

- Suspected adverse reaction
- Unexpected
- Serious

If the AE does not meet all three of the definitions, it should not be submitted as an expedited IND safety report.

The timeline for submitting an IND safety report to FDA is no later than **15 calendar days** after the Investigator determines that the suspected adverse reaction qualifies for reporting (21 CFR 312.32(c)(1)).

Any unexpected fatal or life-threatening suspected adverse reaction will be reported to FDA no later than **7 calendar days** after the Investigator's initial receipt of the information (21 CFR 312.32(c)(2)).

Any relevant additional information that pertains to a previously submitted IND safety report will be submitted to FDA as a Follow-up IND Safety Report without delay, as soon as the information is available (21 CFR 312.32(d)(2)).

